## 12.2 Institutional Review Board Approval Requirements

This study is to be submitted to the IRB applicable for each of the study sites for review and approval prior to enrolling subjects. The Investigator is responsible for keeping approval current and maintaining appropriate correspondence and reports.

Copies of all IRB applications, approval letters, Informed Consent Forms (ICF) and other correspondence are to be sent to the Sponsor, with originals kept in the Site Study Regulatory Binder.

## 12.3 Withdrawal of IRB Approval

The Investigator is to notify the Sponsor of any withdrawal of IRB approval within 5 working days of such occurrence. If the IRB terminates or suspends its approval of the Study, the Investigator will promptly notify Sponsor and provide a detailed written explanation of the termination or suspension. Upon receipt, the Sponsor will provide written guidelines/instructions on subject withdrawal/termination processes and timelines.

## 12.4 Management of Protocol Revisions/Amendments

All changes and updates to this protocol will be initiated by the GE Healthcare study team. The team will also determine the impact to the study and other study documents.

Any protocol amendments and/or study document revisions will be submitted to the Institutional Review Board and the U.S. FDA as IDE supplements for approval as required.

Site training will be documented and filed in the site's Study Regulatory Binder and in the Clinical History file along with the protocol amendment and/or study document revisions, as well as IRB submission(s) and approval(s).

## 12.5 Informed Consent and Privacy Requirements

Informed consent will be obtained from all subjects prior to participation in the study, per the determination of the IRB. The IRB shall formally approve the study's Informed Consent Form (ICF).

Informed consent will be documented in the source record of each subject. The Investigator or designee will consent the subject per regulatory guidelines which include the subject has ample time to review the ICF and have all questions answered to their satisfaction; the subject may take the ICF home to review with family members or others prior to agreeing to participate in the study; upon agreeing to participate in the study, the subject signs and dates the document while initialing any indicated lines; the person who consented the subject signs and dates the document; the Investigator signs and dates the document.

**Study Title:** Multi-site Anesthesia randomized controlled Study of End tidal control (Et Control) compared to conventional anesthesia Results (MASTER-Anesthesia Trial)  
**Study No:** 123.07-2015-GES-0002

GE Healthcare

The subject will be given a copy of the signed informed consent form and the original will be retained with study files.

The subject will also be given information explaining his/her protection and rights under the Health Insurance Portability and Accountability Act (HIPAA) requirements.

## 12.6 Investigator Progress and Final Report

The Principal Investigator shall submit progress reports to the Sponsor and reviewing IRB annually at a minimum. The investigator shall submit a final report within three months after termination or completion of the investigation to the Sponsor and the reviewing IRB.

## 12.7 Sponsor Reporting

### 12.7.1 FDA Withdrawal

The Sponsor shall notify all reviewing IRBs and investigators of any withdrawal of FDA approval within five (5) working days.

### 12.7.2 Investigator List

The Sponsor shall submit to FDA at 6-month intervals, after initial IDE approval, a current list of the names and addresses of all participating investigators.

### 12.7.3 Progress Reports

The Sponsor shall submit progress reports to the FDA and all IRBs at least annually.

### 12.7.4 Final Report

The Sponsor shall notify FDA within 30 working days of the completion or termination of the investigation. The Sponsor shall submit a final report to FDA, IRBs and participating investigators within 6-months of completion or termination of the investigation.

## 13. DATA SAFETY MONITORING BOARD

A Data Safety Monitoring Board (DSMB) will be utilized for this study to provide additional assurance of subject safety.

The DSMB shall consist of three (3) members. The members shall be composed of two (2) clinicians with clinical expertise in anesthesia, and one (1) biostatistician knowledgeable in statistical methods for clinical trials and sequential analysis of clinical trial data.

Members of the DSMB shall have relevant experience in clinical trials, and do not have scientific, financial, personal, or other conflicts of interest related to the conduct of this

**Study Title:** Multi-site Anesthesia randomized controlled Study of End tidal control (Et Control) compared to conventional anesthesia Results (MASTER-Anesthesia Trial)  
**Study No:** 123.07-2015-GE5-0002

GE Healthcare

clinical trial. The chairperson of the DSMB should have prior experience serving or chairing a DSMB.

The DSMB shall hold meetings at regular intervals or ad hoc, as needed, and will be detailed in the DSMB Charter. The DSMB may make recommendations on the basis of the following established enrollment stopping/pausing criteria (*also noted in Section 11.2—Criteria for Early Termination or Suspension of the Study*) to ensure subject safety:

- If three (3) subjects in the Et Control Arm of the study have a Serious Adverse Event (SAE or an Unanticipated Adverse Device Effect (UADE) at any point in the study.
- At the discretion of the DSMB, any determination that the safety data indicates the study is not safe to continue.
- If the Sponsor is notified of two early subject terminations (*Section 11.1*) or the study stopping criteria (*Section 11.2*) is met, the Sponsor will notify all study sites to pause enrollment and the DSMB shall convene an ad hoc meeting to determine if the terminations were device related safety issues.

The Sponsor's medical monitor shall review the DSMB's findings and determination, and make the decision, if necessary, to stop the study to ensure subject safety.

## 14. DATA AND QUALITY MANAGEMENT

### 14.1 Management of Data

Data management processes for handling study data will be maintained by the Sponsor.

Upon enrollment, all subjects will be assigned a subject number and a randomization code. Electronic Case report forms (eCRFs) will use subject numbers only and will not include subject names or other identifiable personal information.

The Sponsor and/or its authorized representatives may use data collected in this study for future technology development, marketing purposes, publications, or other possible uses. Specifically, any data obtained in this study may be used as part of a regulatory submission.

The approved Data Management Plan (DMP) will be located in the study's Clinical History File (CHF) maintained by the Sponsor.

### 14.2 Subject De-identification

Data will be collected from subjects enrolled in this study and entered into eCRFs provided by GE Healthcare (GEHC). Data collected will be labeled with a de-identified Subject Identification Designation (SID), which consists of the Site number and subject number. eCRFs will not contain any identifiable personal information.

The clinical trial site will maintain a Subject Identification Log, which is a list of all subjects who are enrolled in the study, along with their address and medical record number in the

**Study Title:** Multi-site Anesthesia randomized controlled Study of End tidal control (Et Control) compared to conventional anesthesia Results (MASTER-Anesthesia Trial)  
**Study No:** 123.07-2015-GE5-0002

GE Healthcare

event that they must be contacted in the future. *The Sponsor will not take a copy of the Subject Identification Log.*

### 14.3 Completion of Electronic Case Report Forms (eCRFs)

Subject data will be recorded in source documents such as the subject's medical record or study-specific worksheets. Data will then be entered into eCRFs by site personnel. The eCRFs will be reviewed by the Sponsor's designated clinical monitor and then transmitted by the monitor to the Contract Research Organization's (CRO) electronic database. All data entered into the eCRF should be verifiable with source documents unless the eCRF is the source itself. The data collected from the Aisys CS anesthesia machine and from the EMR will be saved onto CD/DVD or USB drives and transferred to the (CRO) to store the raw data for later evaluation.

To ensure the quality and integrity of the data, it is the responsibility of the Principal Investigator or designee to enter data into the eCRFs for each enrolled subject in a timely manner. GEHC will provide eCRFs and will train study staff on data entry using Good Documentation Practices (GDP). eCRF completion guidelines may be provided by the Sponsor to help facilitate training. eCRFs will be completed as information becomes available.

During the course of monitoring, if any errors or omissions are found, they shall be brought to the attention of the site designee, who shall make the corrections, as appropriate on the eCRFs. In the event of an eCRF audit or data review once the eCRFs have been completed, a data query will be generated and the error, omissions or clarifications will be corrected on the associated eCRF.

The Principal Investigator or a Sub-Investigator will electronically sign and date the indicated places on the eCRF. This signature will indicate that a thorough inspection of the data has been made and will thereby certify the contents of the form.

### 14.4 Data Handling and Record Keeping

All documents and data shall be produced and maintained in a manner that assures control and traceability.

### 14.5 Record Retention at the Site

All records pertaining to the conduct of the study, including source data, eCRFs, electronic data ICFs, IRB correspondence, and other study documentation must be retained at the site for inspection at any time by the Sponsor's authorized Study Monitor or designee or regulatory agency; i.e., US Food and Drug Administration (USFDA). These records will be maintained by the site for a minimum of 2 years, per US FDA 21 CFR Part 812.140(d), or a maximum of 3+ years, according to the Sponsors policies; after the investigation termination date or after the date the records are no longer required for purposes of supporting a

**Study Title:** Multi-site Anesthesia randomized controlled Study of End tidal control (Et Control) compared to conventional anesthesia Results (MASTER-Anesthesia Trial)  
**Study No:** 123.07-2015-GE5-0002

GE Healthcare

premarket approval application or notice of completion of a product development protocol. Elements should include the following:

- **Source data and documentation:** relevant to data recorded for subject screening and eCRF corroboration (i.e., information in original records, certified copies of original records of clinical findings, observations, or other activities for the study)
- **Subject Files:** containing the eCRF worksheets and completed patient eCRFs
- **Regulatory Binder:** containing the protocol and amendments, IRB submissions and approvals, blank and signed/dated ICF(s), and site study logs
- **Reference Manuals:** containing the protocol, responsibilities of the Investigator, Sponsor, AE/SAE and informed consent guidelines, applicable study aids (training material, device screen shots), and central supplier instructions

The Principal Investigator or institution shall provide direct access to source data during and after the clinical investigation for monitoring, audits, IRB review, and regulatory authority inspections.

The Principal Investigator is responsible for storing all study related records until notified by GE Healthcare that they can be destroyed. No source documents or study records will be destroyed without GE Healthcare notification and approval. If records are shipped to an off-site location due to space concerns, GE Healthcare must be notified of the change of location.

## 15. MONITORING PLAN

### 15.1 Brief Description

In collaboration with the site, the Sponsor will ensure proper monitoring of the study to confirm that all the clinical requirements are met. There will be a minimum one monitoring visit made to each participating site after enrollment commences. Monitoring visits will ensure adherence to the protocol, completion of informed consents, IRB review of the study, maintenance of records, primary outcomes review and review of the eCRFs and source documentation for accuracy and completeness.

Other monitoring visits will be determined by GE Healthcare study team on an as needed basis. Remote data collection and monitoring may be completed on a pre-determined schedule.

During monitoring, the Sponsor will conduct 100% source data verification on all data collection on the eCRFs. Source data verification will not be completed on data collected electronically from the anesthesia machine or electronic medical records, including heart rate, blood pressure, SpO2, Et Control performance parameters (EtO2%, EtAA%), anesthesia machine settings (device log, anesthetic agent usage, user setting interactions), measured parameters, and alarms.

**Study Title:** Multi-site Anesthesia randomized controlled Study of End tidal control (Et Control) compared to conventional anesthesia Results (MASTER-Anesthesia Trial)  
**Study No:** 123.07-2015-GE5-0002

GE Healthcare

At the Close-out Visit, the monitor will collect all original documents contained in the site's Study Regulatory Binder. All study documents will be filed in the Clinical History File (CHF). Copies will remain in the binder at the site.

## 15.2 Confidentiality and Data Protection

The investigator affirms and upholds the principle of the participant's right to privacy, and the investigator shall comply with applicable privacy laws. Especially, anonymity of the participants shall be guaranteed when presenting the data at scientific meetings or publishing data in scientific journals.

Individual subject medical information obtained as a result of this study will be considered confidential, and disclosure to third parties will be prohibited. Subject confidentiality will be further ensured by utilizing subject identification code numbers. For data verification purposes, authorized representatives of the Sponsor, a competent authority (CA), or an ethics committee (EC) may require direct access to parts of the medical records relevant to the study, including subject medical history.

### 15.2.1 Storage of Collected Data and Associated Health Data

Electronic case report forms (eCRFs), electronic data collected by the Aisys CS Anesthesia Machine, and associated data will be collected and disclosed to the Sponsor as part of this study. Fully de-identified data, which has had all personal identification information of the subject removed, may be stored and used by the Sponsor indefinitely. The Sponsor and/or its authorized representatives may use any de-identified data collected in this study for future technology and engineering development, marketing purposes, education, regulatory submissions, publications, or other possible uses.

### 15.3 Reference to Approved Monitoring Plan

The approved monitoring plan will be located in the study's CHF maintained by the Sponsor.

## 16. PUBLICATION POLICY

Neither the complete nor any part of the results of the study carried out under this protocol, nor any of the information provided by the Sponsor for the purposes of performing the study, will be published or passed on to any third party without the consent of the study Sponsor. Any investigator involved with this study is obligated to provide the Sponsor with complete test results, data derived from the study, and additional clarification, upon Sponsor request.

Data obtained from this study may be used for submission to peer reviewed publications that are consistent with study contracts with prior permission from GE Healthcare. Data may also be used for marketing purposes.

**Study Title:** Multi-site Anesthesia randomized controlled Study of End tidal control (Et Control) compared to conventional anesthesia Results (MASTER-Anesthesia Trial)  
**Study No:** 123.07-2015-GES-0002

GE Healthcare

## 18. GLOSSARY OF TERMS

Air	Medical Air
Adverse Device Effect (ADE)	An adverse event related to the use of an investigational medical device [ISO 14155:2011 3.1]. This includes any adverse events resulting from insufficient or inadequate instructions for use, deployment, implantation, installation, or operation, or any malfunction of the investigational medical device. This includes any event that is a result of a user error or intentional misuse of the investigational device [ISO 14155:2011 3.43].
Adverse Event (AE)	As defined by EN ISO 14155-2011: any untoward medical occurrence, unintended disease or injury, or untoward clinical signs (including abnormal laboratory findings) in subjects, users or other persons, whether or not related to the investigational medical device.
Anticipated Adverse Device Effect	Any adverse event and/or reaction, the specificity or severity of which is consistent with the IRB approved informed consent, protocol, investigator brochure, or product labeling.
Balance gas	Remaining carrier gases other than oxygen delivered to the patient
Circle rebreathing system	An anesthesia breathing system with a gas reservoir that allows patient gases to be rebreathed after the expired carbon dioxide is removed.
Clinician	Specialty clinician trained in the administration of anesthesia care, including anesthesiologists, residents, fellows, CRNA, or certified anesthesia assistant.
Closed circuit anesthesia	Functional mode of circle breathing system with fresh gas flow equal to patient gas uptake
Device deficiency	An inadequacy of a medical device with respect to its identity, quality, durability, reliability, safety, or performance, such as malfunctions, use errors, and inadequate labelling [ISO 14155:2011 3.15].
Early termination of a subject	Any situation in which the clinician determines they no longer want to continue with the case, or the clinician may choose to discontinue the Et Control mode during a case.
End tidal Concentration	Gas concentration at the end of expiration
End of surgery	Often defined as the procedure end time, last stitch, or placement of the last bandage
Et Control (called Smartflow in feasibility study)	A mode of adjusting the mixer and vaporizer delivery based set target of end-tidal anesthetic agent and oxygen concentrations
Evaluable Population	This analysis set includes all randomized subjects with at least 45 minutes of inhalational anesthesia data collected during the study procedure.
Fresh gas	Combined gases from the mixer and vaporizer
Gender	Biological sex of the subject.
Heart rate	Defined as the heart rate < 45bpm or > 110bpm for more than 5 minutes.

**Study Title:** Multi-site Anesthesia randomized controlled Study of End tidal control (Et Control) compared to conventional anesthesia Results (MASTER-Anesthesia Trial)  
**Study No:** 123.07-2015-GE5-0002

GE Healthcare

High flow anesthesia	Anesthesia delivery with fresh gas flow above minute ventilation typically above 5 liters per min
Hypoventilation	Inadequate ventilation delivered to the patient
Hypoxia	Insufficient oxygen delivered to the patient defined as for SpO 2 , for data collected every five minutes any single incidence of SpO 2 readings less than 90%.
Induction Time	Start: Aisys CS  recording F i O 2 > 80% (pre-oxygenation) with end-tidal CO 2 breaths detected. End: When the subject is intubated (LMA or endotracheal) and when mechanical ventilation is turned on.
Intent-to-treat Population	This analysis sets includes all randomized subjects.
Low flow anesthesia	Anesthesia delivery with fresh gas flow of about 1 to 3 liter per min
Mechanical ventilation	Ventilation delivered by an anesthesia ventilator
Medium flow anesthesia	Anesthesia delivery with fresh gas flow of about 3 to 5 liter per min
Minimal flow anesthesia	Anesthesia delivery with fresh gas flow of about 0.5 to 1 liter per min
Minimum Alveolar Concentration	A concept used to compare the potency of anesthetic vapor. It is defined as the concentration of the vapor in the lungs that is needed to prevent movement (motor response) in 50% of subjects in response to surgical (pain) stimulus
Minute ventilation	Patient volume ventilation per minute
Mixer	A device used to control the flow of oxygen mixed with air or nitrous oxide
Non-Invasive Blood pressure (NIBP)	Defined as having the systolic blood pressure (SBP) reading < 75 mmHg or > 160 mmHg or mean arterial pressure (MAP) of < 55 mmHg or > 120 mmHg for > 5 minutes.
Non rebreathing system	A breathing system where the patient inspired gases is totally supplied by the gas mixer and the vaporizer.
OR discharge	Patient disconnected from the anesthesia machine
Peripheral Capillary Oxygen Saturation (SpO 2 )	Defined as having a value less than 90% for more than 5 minutes.
Per Protocol Population	This analysis set includes all subjects in the evaluable population without critical protocol deviation.
Post-anesthesia discharge time	From the OR discharge to discharge time from the PACU ( the time patient meets criteria to discharge from PACU ).
Predicted Total Lung Capacity	An estimated lung capacity based on sex and height
Pre-existing Hypertension	Patient that has been treated for hypertension
Rebreathing system	A breathing system where expired patient gases are allowed to recirculate and rebreathed. Rebreathed gases mix with the gases supplied by the mixer and vaporizer to form the inspired patient gases.
Safety Population	This analysis set includes all randomized subject, who underwent

**Study Title:** Multi-site Anesthesia randomized controlled Study of End tidal control (Et Control) compared to conventional anesthesia Results (MASTER-Anesthesia Trial)  
**Study No:** 123.07-2015-GE5-0002

GE Healthcare

	anesthesia using the investigational device or the control device.
Serious Adverse Device Effect (SADE)	An adverse device effect that has resulted in any of the consequences characteristic of a serious adverse event [ISO 14155:2011 3.36].
Serious Adverse Event (SAE)	As defined by EN ISO 14155 – 2011: an adverse event that 
 
a. led to death;
 
b. led to a serious deterioration in the health of the subject, that either resulted in:           
 
(1) a life-threatening illness or injury, or
 
(2) a permanent impairment of a body structure or a body function, or
 
(3) in-patient or prolonged hospitalization, or
 
(4) medical or surgical intervention to prevent life-threatening illness or injury or permanent impairment to body structure or a body function;
 
 
 
c. led to fetal distress, fetal death or a congenital abnormality or birth defect.
 

Time of last breath from the anesthesia machine	Point of last breath from the data collection
Unanticipated adverse device effect (UADE)	As defined by 21 CFR 812.3: means any serious adverse effect on health or safety or any life-threatening problem or death caused by, or associated with, a device, if that effect, problem, or death was not previously identified in nature, severity, or degree of incidence in the investigational plan or application (including a supplementary plan or application), or any other unanticipated serious problem associated with a device that relates to the rights, safety, or welfare of subjects.
Unanticipated serious adverse device effect (USADE)	A serious adverse device effect, which by its nature, incidence, severity, or outcome has not been identified in the current version of the risk analysis report [ISO 14155:2011 3.42]. In the United States, any serious adverse effect on health or safety or any life-threatening problem or death caused by, or associated with, a device, if that effect, problem, or death was not previously identified in nature, severity, or degree of incidence in the study documents, will be reported in accordance with 21 CFR 812.3 and applicable laws and regulations.
Unrecoverable failure	The inability to use Et Control mode because of unrecoverable device malfunction
Vaporizer	A device used to vaporize and meter the concentration output of volatile anesthetics added to the mixer gases.

**Study Title:** Multi-site Anesthesia randomized controlled Study of End tidal control (Et Control) compared to conventional anesthesia Results (MASTER-Anesthesia Trial)  
**Study No:** 123.07-2015-GE5-0002

GE Healthcare

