## 10.2 Adverse Event Definitions

**Adverse Event (AE):** As defined by EN ISO 14155-2011: any untoward medical occurrence, unintended disease or injury, or untoward clinical signs (including abnormal laboratory findings) in subjects, users or other persons, whether or not related to the investigational medical device.

**NOTE:** *This definition includes events related to the investigational medical device or the comparator. This definition includes events related to the procedures involved.*

Given the frequency at which physiological changes occur during the course of general anesthesia, the following definitions for changes in blood pressure, heart rate, and oxygenation will be used to determine adverse event reporting. If any of the parameters reach the below thresholds they shall be reported to the Sponsor as adverse events.

- (1) **Non-Invasive Blood pressure (NIBP):** defined as having the systolic blood pressure (SBP) reading < 70 mmHg or > 160 mmHg or mean arterial pressure (MAP) of < 55 mmHg or > 120 mmHg for > 5 minutes.
- (2) **Peripheral Capillary Oxygen Saturation (SpO2):** defined as having a value less than 90% for more than 5 minutes.
- (3) **Heart rate:** defined as the heart rate < 45bpm or > 110bpm for more than 5 minutes.

Additional adverse events related to physiological changes can be reported at the clinician's discretion.

**Serious Adverse Event (SAE):** As defined by EN ISO 14155-2011: an adverse event that

- a. led to death;
- b. led to a serious deterioration in the health of the subject, that either resulted in:
  - (1) a life-threatening illness or injury, or
  - (2) a permanent impairment of a body structure or a body function, or
  - (3) in-patient or prolonged hospitalization, or
  - (4) medical or surgical intervention to prevent life-threatening illness or injury or permanent impairment to body structure or a body function;
- c. led to fetal distress, fetal death, or a congenital abnormality or birth defect.

**NOTE:** *Planned hospitalization for a pre-existing condition, or a procedure required by the Clinical Investigation Plan (clinical protocol), without serious deterioration in health, is not considered a serious adverse event.*

**Anticipated Adverse Device Effect:** Any adverse event and/or reaction, the specificity or severity of which is consistent with the IRB approved informed consent, protocol, investigator brochure, or product labeling.

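### The Glossary's low systolic limit and its Hypoxia entry do not match the adverse-event definitions in Section 10.2

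*Combined protocol and SAP*

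**What the plan says.** Section 10.2 gives the reporting rule for vital signs: "If any of the parameters reach the below thresholds they shall be reported to the Sponsor as adverse events". The limits follow. Blood pressure (NIBP) is "defined as having the systolic blood pressure (SBP) reading < 70 mmHg or > 160 mmHg". The same item adds limits on mean pressure, under 55 and over 120 mmHg, and closes with a duration of over 5 minutes. Saturation is "defined as having a value less than 90% for more than 5 minutes". The heart-rate limits are under 45 and over 110 bpm, again lasting over 5 minutes.

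Section 18 (Glossary) defines the same items again. Its NIBP entry begins "Defined as having the systolic blood pressure (SBP) reading < 75 mmHg or > 160 mmHg" and then gives the same mean-pressure limits and duration as Section 10.2. Its SpO2 entry reads "Defined as having a value less than 90% for more than 5 minutes". Its heart-rate entry agrees with Section 10.2. A separate entry for Hypoxia uses the words "for data collected every five minutes any single incidence of"; what it counts is a saturation value under 90%, and it sets no duration.

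Four other places bear on this:

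- The note at the end of Section 10.3 says that NIBP, SpO2 and heart-rate events are reported by the Section 10.2 definition.
- Table 10-1 lists hypoxia as an anticipated event, without a numerical definition.
- Section 8.1.7 analyzes a subset of vital-sign adverse events covering NIBP, SpO2 and heart rate. It also analyzes adverse events by hypertension and ASA status.
- Section 6.3.2 asks for readings at least every 2.5 minutes in the first 2 hours and at least every 5 minutes after that.

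**The concern.** A numerical limit that decides whether an episode is an adverse event appears with two values in the current text, and one saturation term carries a duration rule that its neighbours do not share. The conflict lies between sections now in force and does not rest on the amendment appendices.

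Adverse events are the only safety endpoint in Section 3.4.2. In the feasibility study all nine adverse events were hypotension, 6 with Et Control and 3 with control (Section 1.2.3). With counts of that order, reclassifying a few episodes could change how a comparison of hypotension looks.

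Clinicians and investigators know the arm (Section 4.2). Source data verification is not done on the EMR pressures, saturations and heart rates (Section 15.1). If staff can choose between two definitions, the choice is unlikely to be noticed and need not be the same in both arms.

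**Working it through.** The plan states no figure to reproduce. The check sets the definitions side by side and finds where they disagree.

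**Step 1. Compare the limits.**

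| Item | Section 10.2 | Glossary | Agree? |
|---|---|---|---|
| Low systolic | < 70 mmHg | < 75 mmHg | No |
| High systolic | > 160 mmHg | > 160 mmHg | Yes |
| Mean pressure (MAP) | < 55 or > 120 mmHg | < 55 or > 120 mmHg | Yes |
| Blood-pressure duration | > 5 min | > 5 min | Yes |
| Saturation, SpO2 entry | < 90% for > 5 min | < 90% for > 5 min | Yes |
| Saturation, Hypoxia entry | no such term | any single reading < 90% | No, in duration |
| Heart rate | < 45 or > 110 bpm for > 5 min | same | Yes |

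**Step 2. Blood pressure.** I read the duration as applying to the systolic and the mean-pressure limits alike. The rules are then:

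- Section 10.2: event if duration > 5 and (SBP < 70 or SBP > 160 or MAP < 55 or MAP > 120).
- Glossary: the same, with SBP < 75 in place of SBP < 70.

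They differ exactly when duration > 5, 70 ≤ SBP < 75 and 55 ≤ MAP ≤ 120. Evaluating both rules at whole numbers (SBP 50 to 180, MAP 30 to 139 and below SBP, durations 4, 5, 6 and 11 minutes) gives disagreement only at SBP 70 to 74, MAP 55 to 73, and 6 or 11 minutes. In every such case the Glossary gives an event and Section 10.2 does not.

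Example: SBP 72, MAP 57, 6 minutes. Under Section 10.2, 72 is not below 70 and 57 is not below 55, so there is no event. Under the Glossary, 72 is below 75, so there is one.

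To see how wide this zone is, assume MAP = DBP + (SBP − DBP)/3, a formula the documents do not give. Then MAP ≥ 55 needs DBP ≥ 1.5 × (55 − SBP/3):

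- SBP 70: 1.5 × (55 − 23.33) = 47.5 mmHg
- SBP 74: 1.5 × (55 − 24.67) = 45.5 mmHg

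With a lower diastolic pressure, MAP is below 55 and both rules give an event. The zone is narrow.

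**Step 3. Saturation.**

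| Recorded SpO2 | Lasting | Section 10.2 | Glossary SpO2 entry | Glossary Hypoxia entry |
|---|---|---|---|---|
| 88% | 2.5 min | no | no | yes |
| 88% | 5 min | no | no | yes |
| 88% | 6 min | yes | yes | yes |
| 90% | 10 min | no | no | no |

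The 90% cut-off is common to all three. Only the Hypoxia entry drops the duration, so the Glossary conflicts with Section 10.2 and with itself. That entry also presumes five-minute data, which does not fit the 2.5-minute readings of the first 2 hours.

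**Step 4. Which text governs.** For reporting NIBP, SpO2 and heart-rate events, Section 10.3 names Section 10.2. It does not name Hypoxia. For analysis, Section 8.1.7 uses the term NIBP, which Section 10.2 and the Glossary define differently, and cites neither.

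**The case against.** The strongest reply is that the protocol already says which definition controls. Section 10.3 names Section 10.2, and Section 10.2 holds the only instruction to report; the Glossary has none. The Glossary's SpO2 entry agrees with Section 10.2, and Table 10-1 attaches no threshold to hypoxia, so the Hypoxia entry has no stated route into the Section 8.1.7 subset. Safety lies outside the ordered hypothesis tests (Section 8.1.2) and the pass/fail criterion (Section 8.4). Randomization is stratified by Investigator (Section 6.1), so an investigator who applies one definition consistently applies it in both arms. Section 10.2 also lets clinicians report other physiological changes at their discretion, so some variation is accepted already. The five-minute wording fits the part of a case after the first 2 hours.

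Most of this stands, and it makes the effect small. Three things remain:

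- The precedence note covers reporting of three named parameters. It does not cover Hypoxia or the analysis subset, and the Glossary does not say that it yields to Section 10.2.
- The discretionary clause leaves a way for a single low reading to be reported as Hypoxia.
- Stratification balances consistent habits between arms. It does not protect against use of the definitions that varies with the known arm.

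**Conclusion.** The contradiction is real but limited. One blood-pressure number differs (70 against 75 mmHg, low systolic), and one Glossary term drops the saturation duration. The affected episodes are those with SBP from 70 to below 75 mmHg and MAP from 55 to 120 mmHg for more than 5 minutes, and recorded SpO2 readings below 90% lasting 5 minutes or less if someone classes them as Hypoxia. Their frequency cannot be worked out from the documents. The result assumes that the stated duration applies to both pressure limits; the diastolic figures also rest on the assumed formula for mean pressure.

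A reader might infer that every short saturation dip is classified differently by the Glossary. The documents do not support that: the Glossary's SpO2 entry treats such dips as Section 10.2 does, and the Hypoxia entry counts only readings that were recorded.

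A reader might also infer that the main safety comparison is compromised. That goes too far. Section 8.1.7 first compares the percentage of subjects with any adverse event, the vital-sign events are a subset, and nothing in the documents shows a difference between arms in how the definitions would be used.

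**What to change.** Reconcile Section 10.2, the Glossary entries for NIBP and Hypoxia, and the use of hypoxia in Table 10-1, so that each limit and duration is stated once and the Glossary refers to it. Which values to keep is for the sponsor and its clinical advisers; this review does not choose them.

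Then have Section 8.1.7 derive the NIBP, SpO2 and heart-rate event subset by program from the EMR readings against that single definition, identically in both arms, and show it beside the investigator-reported events. The correction of the text does not depend on this second step. Its purpose is to free the subset from an unblinded choice between definitions.

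The program needs a written rule for turning spaced readings into a duration. Three consecutive readings 2.5 minutes apart span 2 × 2.5 = 5 minutes, and two readings 5 minutes apart also span 5 minutes, so neither run by itself exceeds 5 minutes.

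The cost is a protocol clarification and modest programming on readings that Section 6.3.2 already collects.
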